6.13.3 Clinical Laboratory Evaluations

Clinical laboratory evaluations (including clinical chemistry panel [fasted at least 8 hours on designated study days], coagulation parameters, haematology, and UA; [Appendix B](#)) will be collected at the time points specified in [Table 6-1](#). Medically indicated laboratory tests (emergency or unscheduled tests) will be conducted at the local laboratory as needed.

A blood sample will be taken from each subject for haematology, coagulation, and serum chemistry analysis at the time points delineated in the study schedules. Additional clinical laboratory tests may be performed at other times if deemed necessary.

Urinalysis will be performed at the Screening visit and at other times according to the study schedule. Urine microscopy will be performed in the event of abnormal macro analysis.

Screen for a hepatitis panel and TB testing ([Appendix C](#)) will be performed at Screening. Stool samples for *C. difficile* (confirmed by toxin result), culture, and ova, and parasite

examination will be obtained at Screening. An HIV antibody test will not be performed, but history of positive HIV test is exclusionary. Serum and urine pregnancy tests (WOCBP only) will be performed at the time points specified in [Table 6-1](#).

6.13.4 Vital Signs

Vital sign measurements (including oral temperature, respiratory rate, and BP and pulse) will be obtained at the time points specified in [Table 6-1](#). Blood pressure and pulse will be taken with the subject in a supine or semi-recumbent position; subjects will have rested in a supine or semi-recumbent position for at least 5 minutes prior to and during vital sign measurements. Temperature may be taken by oral, axillary, or tympanic route provided the same route is used for the participant throughout the study. When the time of vital sign measurements coincides with a blood draw, the vital signs will be taken before the scheduled blood draw where possible.

6.13.5 Twelve-lead Electrocardiograms

A 12-lead ECG will be obtained at the time points specified in [Table 6-1](#). Additional ECG monitoring may be performed at other times if deemed necessary. Subjects will be supine or semi-recumbent for at least 5 minutes prior to obtaining an ECG measurement.

The predose (baseline) ECG will be repeated 3 times with 1- to 2-minute intervals between ECG readings within 2 hours prior to dosing. The ECG measurements will be single measurements performed according to the study schedule. Electrocardiogram parameters (including heart rate; PR, QRS, and QT intervals; and QT interval corrected for heart rate using Fridericia's formula) and the Investigator's overall interpretation of the ECG will be recorded in the CRF. When the time of ECG monitoring coincides with a blood draw, the ECG will be taken before the scheduled blood draw.

6.13.6 Physical Examinations

A complete physical examination will be performed at the time points specified in [Table 6-1](#). A directed exam (including exam of general appearance, skin, thorax/lungs, cardiovascular system, and abdomen) will be performed at the time points specified in [Table 6-1](#).

The time and date of the physical examination findings will be recorded in the CRF and any clinically significant findings will be recorded as AEs.

6.14 Study Termination

The study or specific participating sites may be terminated if significant violations of Good Clinical Practice (GCP) that compromise the ability to achieve the study objectives or compromise participant safety are observed at any time during the study. With regard to safety, the study may be temporarily suspended or terminated should the DMC determine that the safety of study participants is significantly jeopardised. Additional reasons for termination of the study may include: medical or ethical reasons affecting continued performance of the study, inability to recruit subjects, or suspension or cancellation of the drug development program. The decision for a temporary or permanent study hold will depend on the nature, frequency, and severity of AEs that were observed in all enrolled participants to date. In a temporary study hold, no additional participants will be enrolled into the study or dosed with study drug until the DMC determines it is safe to proceed with the study.

7 DATA ANALYSES AND SAMPLE SIZE

7.1 Sample Size

Approximately 240 male and non-gravid female subjects aged 18 to 80 with moderate to severe active UC will be randomised. If only 2 arms are selected for continuation following the IA, then up to approximately 210 subjects will be randomised in the study; see [Section 7.2](#).

Prior studies^{1,17-21} suggest treatment effects of approximately 21 percentage point differences from placebo clinical remission rate of approximately 10%. Those values were assumed for purposes of design of this 12-week trial.

The table below shows power for representative scenarios of potential TRUE underlying dose-response relationships, as well as that for no drug effect to assess type 1 error (calculations via Cytel's EAST COMPASS adaptive dose-finding software based on 1000 simulations of each design, with each simulated trial analysed as described in the statistical methods section).²²

TRUE underlying response rates				power (alpha=0.025, 1-sided)			
placebo	150 mg	300 mg	900 mg	N=260	N=240	N=220	N=200
0.1	0.2	0.31	0.31	93%	91%	90%	84%
0.1	0.17	0.24	0.31	83%	82%	78%	75%
0.1	0.1	0.1	0.1	3.4%	2.2%	1.7%	2.1%

7.2 Interim Analysis

An unblinded IA will be performed by the Adaptive Design Review Committee (ADRC) after approximately 60 to 80 subjects have been dosed and completed 12 weeks of dosing or terminated early (Stage 1).²³ A futility analysis will be performed; if the trial does not meet criteria for futility, further analysis will be conducted in order to drop one (or 2) of the PTG-100 dose arms (Stage 1, see below). Following the IA, randomisation will continue to the remaining dose arms (Stage 2).

Conditional power will also be computed at the IA. It is the probability that the trial will yield a statistically significant difference for clinical remission at the higher chosen dose for Stage 2 if the observed difference at the IA is the TRUE underlying difference and the trial is continued to completion. If this probability is low (eg, less than 10% to 20%), the decision could be made to stop the trial for futility.

The PD, efficacy, and safety data will be analysed to model dose- and exposure-response from Stage 1 of the trial to allow dropping of an ineffective or redundant arm(s). Since the trial provides for a 12-week treatment period, it is expected that an additional approximately 60 subjects would be randomised in equal proportions to the 4 treatment groups while the first approximately 60 to 80 subjects' 12-week data are accumulated and analysed. Hence, in Stage 2, the remaining subjects would be randomised in equal proportions to the selected dose(s) and placebo. This would yield approximately 70 to 80 subjects per treatment group for the selected doses. Final analysis will combine all observed data from both Stages 1 and 2.

The IA guidelines for futility and dose selection will be defined in the DMC charter and will be made in consideration of safety data and sound clinical judgment. Dose selection for Stage 2 will be made by the ADRC, which will be comprised of the DMC and a representative of the Sponsor (not involved in the direct conduct of the study). No pre-specified algorithm will be defined for the IA, although specific guidelines for dropping a dose(s) will be provided in the DMC charter. Only the ADRC, which will make the dose selection for Stage 2, and the Independent Statistical Centre, which will perform the IA, will be unblinded.

Stratification by prior treatment with TNF- α antagonist use will be maintained in both Stage 1 and 2.

7.3 Study Populations

Safety Population: All randomised participants who receive any amount of study drug will be included in the safety analyses.

Pharmacokinetic Analysis Population: All randomised participants who receive a Day 0 dose of study drug and who have sufficient PK data (meeting the required minimum blood volume collected along with the sampling schedule, with an accurate record of dosing and sampling time, and without vomiting) for analysis will be included in the PK analyses.

Full Analysis Set: All randomised participants who receive any amount of study drug and who have results from baseline and from ≥ 1 post-baseline assessment will be included in the PD and efficacy analyses.

7.4 Statistical Analysis of Efficacy Data

The primary efficacy endpoint for this study is the proportion of subjects receiving PTG-100 with clinical remission at Week 12 compared with placebo.

Clinical remission is defined as follows, using the Mayo subscores of stool frequency, rectal bleeding, and endoscopy:

- Stool frequency subscore of 0 or 1 with a pre-specified change of 1 or more from baseline
- Rectal bleeding subscore of 0
- Endoscopy subscore of 0 or 1 (modified so that a score of 1 does not include friability)

The secondary endpoints, all based on comparison of individual PTG-100 dose levels with placebo, include:

1. Proportion of subjects with endoscopic response at Week 12 (Day 84) (defined as an endoscopic subscore of 0 or 1)
2. Proportion of subjects with clinical response at Week 12 (Day 84) (defined as at least 1 point and 30% reduction from baseline in rectal bleeding and stool frequency subscores)
3. Mean change in endoscopy subscore from baseline to Week 12 (Day 84)
4. Mean change in rectal bleeding and stool frequency subscores from baseline to Weeks 2, 4, 6, 8, 10, 12, and 16 (Days 14, 28, 42, 56, 70, 84, and 112)

5. Proportion of subjects with endoscopic remission at Week 12 (Day 84) (defined as an endoscopic subscore of 0)
6. Mean change in complete Mayo Score (including all 4 subscores) from baseline to Week 12 (Day 84)
7. Mean change in partial Mayo Score (excluding endoscopy subscore) from baseline to Weeks 2, 4, 6, 8, 10, 12, and 16 (Days 14, 28, 42, 56, 70, 84, and 112)
8. Mean change in faecal calprotectin levels from baseline to Weeks 6, 12, and 16 (Days 42, 84, and 112)
9. Mean change in IBDQ score from baseline to Week 12 (Day 84)

The exploratory endpoints (all based on comparison of individual PTG 100 dose levels to placebo) include:

1. Mean change in histological score from baseline to Week 12 (Day 84) (assessment tool to be determined)
2. Effects of ADA on PK, safety, and efficacy in subjects with positive ADA

Descriptive statistics will be used to evaluate differences in demographic and baseline characteristics.

For the primary analysis, proportions of subjects with clinical remission will be compared between each dose and placebo using Cochran-Mantel-Haenszel test, with adjustment for stratification factors. Rates of clinical response, endoscopic response, and endoscopic remission will be evaluated similarly.

Multiplicity will be addressed via closed testing procedure with combined p-values computed for each of the 2 stages of the trial (IA and post-IA). Each stage p-value will be adjusted as appropriate by closed testing multiple comparison approach per Simes.²⁴ This approach controls the overall type 1 error at $\alpha=0.025$, 1-sided.

All analyses will be based on combined Stage 1 and Stage 2 data and include data from the dose(s) that is (are) dropped for Stage 2. Exploratory analyses will be carried out to assess consistency of results between Stages 1 and 2. Analyses of other binary endpoints will be carried out similarly.

Subjects who discontinue prematurely will be considered treatment failures.

Changes from baseline complete Mayo Score, partial Mayo Score, rectal bleeding subscore, stool frequency subscore, endoscopic subscore, IBDQ score, and faecal

calprotectin levels will be analysed using repeated measures mixed analysis of covariance model adjusted for treatment, time point, treatment-by-time point interaction, stratification factors, and baseline values. For subjects who withdraw prematurely, the last observation will be carried forward. These analyses will be based on the Stage 1 and Stage 2 combined data for exploratory purposes.

Details regarding the statistical analyses of efficacy data will be provided in the Statistical Analysis Plan (SAP).

7.5 Statistical Analysis of Safety Data

The primary safety endpoint is the proportion of subjects with at least 1 AE comparing individual PTG-100 dosing groups with placebo.

The secondary endpoints (all based on comparison of individual PTG-100 dose levels to placebo) will include:

1. Frequency and type of AEs (affecting $\geq 5\%$ of subjects)
2. Proportion of subjects with at least 1 SAE
3. Number and type of SAEs
4. Frequency of AEs of special interest including serious or opportunistic infection (viral, bacterial, fungal including systemic/gut localization), allergic/drug reactions, immune system disorders, and suspected PML
5. Clinically significant changes in safety labs, ECGs, or physical examination findings (including vital signs).

Continuous safety data will be summarised with descriptive statistics (arithmetic mean, standard deviation [SD], median, minimum, and maximum) by dose level. Categorical safety data will be summarised with frequency counts and percentages by dose level. Adverse events will be coded using the most current Medical Dictionary for Regulatory Activities available, which will be indicated in the Data Management Plan. A by-participant AE data listing, including verbatim term, preferred term, system organ class, treatment, severity, and relationship to study drug, will be provided. The number of participants experiencing treatment-emergent AEs (TEAEs) and number of individual TEAEs will be summarised by treatment group, system organ class, and preferred term. The TEAEs will also be summarised by severity and by relationship to study drug.

Laboratory evaluations, vital signs assessments, and ECG parameters will be summarised by treatment group and protocol-specified collection time point. A summary of change-

from-baseline at each protocol-specified time point by treatment group will also be presented.

Clinically significant changes in physical examinations will be listed for each participant and described in the text of the Clinical Study Report.

Medical history will be listed by subject.

Concomitant medications will be listed by participant and coded using the most current World Health Organization drug dictionary.

Further details regarding presentation and analysis of safety data will be detailed in the SAP.

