6.13 Safety Monitoring

Subjects will be monitored for AEs and concomitant medication use throughout the study. Physical examination (including weight and vital signs), clinical safety labs, PML assessments, and ECGs will be done periodically throughout the study according to the schedule specified in [Table 6-1](#). Safety evaluations may be repeated at the Investigator's (or designee's) discretion.

The following will constitute AEs of special interest that will be monitored at each visit: serious or opportunistic infection (viral, bacterial, fungal including systemic/gut localization), allergic/drug reactions, immune system disorders, and/or suspected PML. Adverse events of special interest will not constitute Investigational New Drug safety reports unless they are defined as serious events and there is evidence suggesting a causal relationship between the drug and the event.

The JCV antibody testing must have been performed and documented on all randomised subjects within 90 days prior to dosing. All subjects will be closely monitored for signs and symptoms of PML through directed questionnaires that assess recent changes in vision, speech, gait, sensation, comprehension, coordination, and personality, with any positive responses prompting objective testing^{1,17} by the Investigator (see [Appendix D](#)).

An independent DMC will be appointed to monitor the safety of the subjects in the study. The DMC will meet approximately quarterly to review the safety data and will make recommendations regarding the continuation, modification, suspension, or termination of the study. Operational guidelines will be specified in the DMC charter.

Every effort will be made to schedule and perform the procedures in accordance with the nominal time, giving considerations to appropriate posture conditions, practical restrictions, and the other procedures to be performed at the same time point. Acceptable

windows for study visits are provided in [Section 6.1](#). The order of priority for scheduling procedures around a time point is (in descending order of priority):

- dosing
- PK blood sampling
- PD blood sampling
- vital sign measurements
- ECGs
- blood and urine samples for clinical laboratories
- physical examinations

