6.13.1 PML Monitoring

Any subject with abnormal neurological examination at Screening will be excluded from participation in the study.

The JCV antibody testing must have been performed and documented on all randomised subjects within 90 days prior to dosing.

All randomised subjects will be closely monitored for signs and symptoms of PML through directed questionnaires that assess recent changes in vision, speech, gait, sensation, comprehension, coordination, and personality, with any positive responses prompting objective testing by the Investigator (see [Appendix D](#)).^{1,17,26,27} All randomised study subjects will be closely monitored for the onset of any new neurological signs or symptoms or suspected PML during treatment and follow-up. The study's monitoring program will include education of site personnel and subjects about the signs and symptoms of PML and will advise subjects to report to designated personnel should they experience any signs and symptoms suggestive of PML.

Study sites will be provided a stepwise algorithm for the action plan for all subjects with suspected PML during the study and follow-up period; details regarding this algorithm will be provided in the study manual. Appropriately qualified site staff will complete the subjective PML checklist using the questionnaire ([Appendix D](#)) at all study visits per the schedule in [Section 6.1](#). If any subject has a positive response based on the PML subjective checklist, the site will immediately schedule a visit where the Investigator will perform the PML objective checklist (involving tests of visual fields, ocular motility, speech, muscle strength, gait, memory, and sensation) per [Appendix D](#) and the study manual. If a study subject has both positive subjective and objective checklists, the subject will be referred to a local neurologist for further evaluation to rule out PML. If

the neurologist cannot rule out PML, the case will be referred to the Independent Adjudication Committee (that will include at least one neurologist) for the final determination of PML.

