APPENDIX D - PROGRESSIVE MULTIFOCAL LEUKOENCEPHALOPATHY (PML) ASSESSMENT^{26,27}

A subjective PML checklist (see table below) is to be administered by appropriately qualified site personnel (Investigator or Study Coordinator) to all subjects at Screening, at the designated time points as noted in [Table 6-1](#), and whenever new neurologic symptoms manifest. For each symptom in the subjective checklist that had positive findings, results of an objective evaluation (see below), administered by the Investigator to assess corresponding neurologic function, are to be recorded on the objective checklist and an AE recorded.

Subjective PML Checklist

Symptoms	"Compared to how you usually feel, have you had a significant change in any of the following?"		If the answer is "Yes", obtain a description of the symptom(s) with examples.	Applicable Objective Test(s): Document results on PML Objective Checklist
	Yes	No		
1. Have you been experiencing any persistent difficulty with your vision such as loss of vision or double vision? Have you been having trouble with reading?				Test visual fields and ocular motility.
2. Have you been experiencing any persistent difficulty speaking or having your speech understood by others?				Casual observation of speech output for dysarthria or aphasia. Ask patients to name a few objects and repeat a multipart phrase.
3. Have you been experiencing any persistent weakness in an arm or a leg?				Test for pronator drift (Barré maneuver) and/or fixation on arm roll. Assess the ability to hop on either foot; foot and finger tapping. Test symmetric muscle strength.
4. Have you noticed yourself regularly bumping into things or having difficulty writing?				Ask for spontaneous writing sample and observe finger to nose, heel to shin, and tandem gait.
5. Have you regularly been experiencing difficulty understanding others?				Ability to follow serial commands (Close your eyes, stick out your tongue, and touch your left finger to your left ear)
6. Have you had persistent problems with your memory or thinking?				Recall of 3 objects over 1 minute with distraction; ability to follow commands.
7. Have you been experiencing any persistent numbness or other loss of sensation?				Test sensation side to side with pinprick.

Objective PML Checklist

Positive Symptom(s)	Applicable Objective Test(s)	Test Result(s)		If test result is abnormal, briefly describe result
		Normal	Abnormal	

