### 4.8.1. Adverse Events

The primary safety endpoint is the proportion of subjects with at least 1 AE comparing individual PTG-100 dose groups with placebo.

Secondary endpoints (all based on comparison of individual PTG-100 dose levels to placebo) will include:

- Frequency and type of AEs (affecting  $\geq 5\%$  of subjects)
- Proportion of subjects with at least 1 SAE
- Number and type of SAEs
- Frequency of adverse events of special interest (AESI) including serious or opportunistic infection (viral, bacterial, fungal including systemic/ gut localization), allergic/ drug reactions, immune system disorders, and PML or new onset neurologic symptoms

Adverse events will be coded using the Medical Dictionary for Regulatory Activities (MedDRA) and displayed in tables and listings using System Organ Class (SOC) and Preferred Term.

Analyses of adverse events will be performed for those events that are considered treatment emergent, where treatment emergent is defined as any adverse event with onset after the administration of study medication through the end of the study visit or any event that was present at baseline but worsened in intensity or was subsequently considered drug-related by the investigator through the end of the study.

Adverse events are summarized by subject incidence rates, therefore, in any tabulation, a subject contributes only once to the count for a given adverse event (SOC or preferred term).

The number and percentage of subjects

- with any treatment-emergent adverse event
- with any treatment-emergent adverse events assessed by the Investigator as related to treatment (definite, probable, or possible relationship)
- with any treatment-emergent serious adverse event
- with treatment-emergent adverse events by severity
- with adverse events affecting  $\geq 5\%$  of subjects within any treatment group across both stages of the study
- with AESI

will be summarized by treatment group and overall. In addition, all active groups will be pooled in the summaries for comparison to placebo. In these tabulations, each subject will contribute

only once (i.e., the most related occurrence or the most intense occurrence) to each of the incidence rates in the descriptive analysis, regardless of the number of episodes.

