## **5. CHANGES TO PLANNED ANALYSES**

As of this date, there have been no changes between the protocol-defined statistical analyses and those presented in this statistical plan.

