Table 14.2.2.7A	Change in IBDQ score from Baseline Over Time (FAS)
Table 14.2.2.7B	Change in IBDQ score from Baseline Over Time (PP)

Table 14.2.2.7C	Change in IBDQ score from Baseline Over Time (Sensitivity Analyses – if Needed)
Table 14.2.2.7A	Change in Histological score from Baseline Over Time (FAS)
Table 14.2.2.7B	Change in Histological score from Baseline Over Time (PP)
Table 14.2.3	Summary of Pharmacokinetic Parameters (PK Population)
Table 14.2.4.1A	Change in $\alpha 4\beta 7$ Receptor Occupancy on Peripheral Blood T cells Over Time (FAS)
Table 14.2.4.1B	Change in $\alpha 4\beta 7$ Receptor Occupancy on Peripheral Blood T cells Over Time (PP)
Table 14.2.4.2A	Summary of $\alpha 4\beta 7$ Receptor Expression on Peripheral Blood T cells Over Time (FAS)
Table 14.2.4.2B	Summary of $\alpha 4\beta 7$ Receptor Expression on Peripheral Blood T cells Over Time (PP)
Table 14.2.4.3A	Change in Peripheral Blood Lymphocytes Over Time (FAS)
Table 14.2.4.3B	Change in Peripheral Blood Lymphocytes Over Time (PP)
Table 14.2.4.4A	Change in $\beta 7$ Positive Cells in Colonic Biopsies Over Time (FAS)
Table 14.2.4.4B	Change in $\beta 7$ Positive Cells in Colonic Biopsies Over Time (PP)
Table 14.2.5.1A	Proportion of Subjects with Positive Neutralizing ADA by Week 12 and Week 16 (FAS)
Table 14.2.5.1B	Proportion of Subjects with Positive Neutralizing ADA by Week 12 and Week 16 (PP)

*Displays of Adverse Events (CSR Section 14.3.1)*

Table 14.3.1.1	Overall Summary of Treatment-Emergent Adverse Events by Treatment Group (Safety)
Table 14.3.1.2	Summary of Treatment-Emergent Adverse Events by System Organ Class, Preferred Term and Treatment Group, Sorted in Descending Frequency according to the Total Column (Safety)

Table 14.3.1.3	Summary of Related/Possibly, Probably and Definitely Related Treatment-Emergent Adverse Events by System Organ Class, Preferred Term and Treatment Group (Safety)
Table 14.3.1.4	Summary of Treatment-Emergent Adverse Events by Severity, System Organ Class, Preferred Term and Treatment Group (Safety)
Table 14.3.1.5	Summary of Treatment-Emergent Serious Adverse Events by System Organ Class, Preferred Term and Treatment Group (Safety)
Table 14.3.1.6	Summary of Most Common ( $\geq 5\%$ within any treatment group) Treatment-Emergent Adverse Events by System Organ Class, Preferred Term and Treatment Group (Safety)
Table 14.3.1.7	Summary of Treatment-Emergent Adverse Events by Preferred Term and Treatment Group (Safety)

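### The SAP's AE-of-special-interest count uses a broader neurological component than the Protocol's suspected PML, declares no change, and plans no count of suspected PML by arm

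*Protocol*

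**What the plan says.** The Protocol names the neurological AESI component three times, in the synopsis safety criteria, in 6.13 and in 7.5, and each time it is suspected PML. Section 6.13, which sets out what constitutes an AESI, has "allergic/drug reactions, immune system disorders, and/or suspected PML". Section 7.5, which makes AESI frequency a secondary safety endpoint compared with placebo by dose, has "allergic/drug reactions, immune system disorders, and suspected PML".

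Protocol 6.13.1 has subjects "closely monitored for the onset of any new neurological signs or symptoms or suspected PML during treatment and follow-up". New neurological findings and suspected PML are thus named as two things to watch for, and only the second is in the AESI list. The same section sets an escalation path: "If a study subject has both positive subjective and objective checklists, the subject will be referred to a local neurologist", with unresolved cases going to an adjudication committee. Under Appendix D, for each positive item on the subjective checklist the results of the objective test "are to be recorded on the objective checklist and an AE recorded".

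SAP 4.8.1 gives the component as "immune system disorders, and PML or new onset neurologic symptoms". It supplies no term list and no link to the checklists. It plans the number and percentage of subjects with an AESI by treatment group. SAP 5 says "there have been no changes between the protocol-defined statistical analyses and those presented in this statistical plan".

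**The concern.** The SAP drops the word suspected and adds a category of symptoms that the Protocol lists separately. A program written from the SAP would count subjects whom the Protocol's endpoint would not clearly count. The resulting rate would be reported as the Protocol's secondary safety endpoint, with nothing in the SAP to warn the reader.

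PML is the risk for which this Protocol builds the most apparatus: JCV antibody testing, repeated checklists, neurologist referral and adjudication. The matching count by arm should be fixed in advance. If it is left to be assembled after unblinding, someone must then decide which neurological AEs amounted to suspicion of PML.

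**Working it through.** The plan states no figure on this point, so there is none to reproduce. The check is a comparison of text, followed by an illustration with assumed rates.

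**1. The definitions side by side**

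| Source | Neurological AESI component |
|---|---|
| Protocol synopsis, 6.13, 7.5 | suspected PML |
| SAP 4.8.1 | PML, or new-onset neurologic symptoms |
| SAP 5 | no change declared |

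**2. Following one event through both documents.** Protocol Table 6-1 schedules the PML assessment at screening, predose on Day 0 (unless done in the previous 14 days), and on Days 14, 28, 42, 56, 70, 84, 112 and 252. Exclusion criterion 13 removes anyone with a positive subjective checklist, so an item that is positive later will nearly always be of new onset. Take a subject who reports persistent numbness on Day 28 and whose objective test is normal. Appendix D requires an AE and a follow-up call one week later, with no neurologist referral. Under SAP 4.8.1 this subject fits the AESI wording. Under Protocol 6.13 and 7.5 the subject is an AESI only if an uncorroborated symptom counts as suspected PML, which the Protocol does not say.

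**3. Whether another planned output recovers the Protocol's count.** SAP 7.1 lists AE Tables 14.3.1.1 to 14.3.1.9, and none is titled for AESIs. Table 14.3.1.2 is the "Summary of Treatment-Emergent Adverse Events by System Organ Class, Preferred Term and Treatment Group, Sorted in Descending Frequency". A preferred term for numbness or weakness appears there, but it does not show whether the objective test was abnormal or the subject was referred. SAP 7.2 has no listing of checklist, referral or adjudication results. Suspected PML by arm cannot be read from any planned output.

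**4. Illustration of dilution (all rates assumed).** Take n = 70 per arm, the lower end of the 70 to 80 in Protocol 7.2, with Protocol-defined AESIs in 2 placebo and 6 drug subjects. Let a fraction q of each arm also report an unrelated new neurological symptom, independently. The rate under the SAP wording is 1 − (1 − a/70)(1 − q), with a = 2 or 6.

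| q | Placebo | Drug | Ratio | Difference (points) |
|---|---|---|---|---|
| 0 | 2.9% | 8.6% | 3.0 | 5.7 |
| 0.5% | 3.3% | 9.0% | 2.7 | 5.7 |
| 1% | 3.8% | 9.5% | 2.5 | 5.7 |
| 5% | 7.7% | 13.1% | 1.7 | 5.4 |
| 10% | 12.6% | 17.7% | 1.4 | 5.1 |
| 15% | 17.4% | 22.3% | 1.3 | 4.9 |

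The difference equals (4/70)(1 − q), so it shrinks only by the factor 1 − q.

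**5. Composition of the neurological component (all rates assumed).** If s is the rate of suspected PML and q that of other new symptoms, the other symptoms make up q/(q + s) of the component, treating the two groups as not overlapping.

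| s | Suspected PML expected in 240 | q = 0.5% | q = 2% | q = 5% | q = 15% |
|---|---|---|---|---|---|
| 0.5% | 1.2 | 50% | 80% | 91% | 97% |
| 1% | 2.4 | 33% | 67% | 83% | 94% |

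The share runs from a third to nearly all, depending on rates that the documents do not give.

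**The case against.** The strongest reply is that the Protocol never defines suspected PML operationally. Section 6.13.1 introduces a stepwise plan for subjects with suspected PML and then describes steps that begin with the subjective checklist. On that reading suspicion starts with a new neurological symptom, and the SAP wording is an attempt to make the term usable. This has some force, but the same section names new neurological findings and suspected PML as alternatives, so the equivalence is not established. If the SAP authors intended it, the SAP should say so.

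Three further replies stand:

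- The Protocol's AESI list is already mixed, combining infections, allergic or drug reactions and immune disorders.
- Wider neurological capture is arguably the cautious direction for safety.
- SAP 7.1 gives table titles only, so the AESI line may sit inside Table 14.3.1.1, and the absence of a title does not prove that categories will be merged.

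A reader might infer that common complaints will swamp the AESI count. The documents do not support this. They give no symptom rates, headache and dizziness are not among the seven checklist items, and those items ask about significant change, mostly in persistent or regular problems. A reader might also infer that the Protocol's endpoint is lost altogether. That goes too far: suspected cases would ordinarily fall inside the broader category, and the individual AEs remain visible in the system organ class and preferred term tables and in the by-subject listings.

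**Conclusion.** The discrepancy is real and can be verified from the text. The SAP's AESI count is broader than the Protocol's secondary safety endpoint, SAP 5 is wrong to report no change, and no planned output gives suspected PML by arm.

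The numerical effect is unknown. It could be slight or could dominate the neurological component. The illustration assumes both the event counts and equal symptom rates in the two arms. It shows a ratio that can fall a good deal while the risk difference hardly moves. If neurological symptoms were in excess on drug, the broader category would show that excess rather than hide it.

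Severity is minor. Under the SAP, formal testing covers the primary and then the secondary efficacy endpoints. AESIs are summarised as counts and percentages, so the primary analysis, alpha and power are unaffected.

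Two further inferences should be resisted. Positive subjective and objective checklists together are the Protocol's trigger for neurologist referral, not its stated definition of suspected PML. And nothing in the documents requires new neurological symptoms to be dropped from special-interest monitoring; whether to keep them there is the sponsor's choice.

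**What to change.** 1. Reconcile the neurological component across Protocol 6.13 and 7.5 and SAP 4.8.1.
2. In SAP 4.8.1, report the Protocol-defined AESI total, with suspected PML on its own line by treatment group. The sponsor should write the counting rule before unblinding and tie it to the checklist, referral and adjudication steps in Protocol 6.13.1 and Appendix D. The rule should say whether findings at the Day 252 telephone call count, since that call is in Protocol Table 6-1 but not in the SAP's schedule of assessments.
3. Report other new-onset neurologic symptoms on a separate line, with a stated list of terms or checklist items.
4. Add to SAP 7.1 a table of AESIs by category and treatment group.
5. Record the difference and the reason for it in SAP 5.

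The cost is SAP wording and one table. The checklist, AE and referral information already arises under the Protocol, so no visit, assessment or sample size changes.
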